## Drug Risks

The tables below show the most common and most serious side effects doctors know about. Keep in mind that there might be other side effects doctors do not yet know about. If important new side effects are found, the study doctor will discuss these with you.

### Telotristat Side Effects

Possible Side Effects of Telotristat are listed below and grouped according to which part of the body to which they relate:

#### Gastrointestinal (relating to the stomach and the intestines)

Very common (in 100 people, more than 10 and up to 100 people may experience):

- Nausea

Common (in 100 people between 1 and 10 may experience):

- Flatulence, abdominal distention, gastrointestinal pain, constipation, abdominal pain/upper and lower abdominal pain

Frequency not reported: Fecaloma (obstruction of the intestine due to fecal blockage)

#### Nervous system

Very common (in 100 people, more than 10 and up to 100 people may experience):

- Headache

#### Hepatic (relating to the liver)

Common (in 100 people between 1 and 10 may experience):

- Increased gamma-glutamyltransferase (GGT) levels (may indicate damage to the liver or bile ducts)

Frequency not reported:

- Elevated lab values including alkaline phosphatase, increased alanine aminotransferase, increased aspartate aminotransferase (which may indicate liver damage)

#### Psychiatric (relating to mental and emotional health)

Common (in 100 people between 1 and 10 may experience):

- Depression

#### Cardiovascular (relating to heart function)

Common (in 100 people between 1 and 10 may experience):

- Peripheral edema (swelling in your lower legs or hands)

#### Metabolic (relating to the biochemical processes that regulate the body's functioning)

Common (in 100 people between 1 and 10 may experience):

- Decreased appetite

#### Other

Common (in 100 people between 1 and 10 may experience):

- Pyrexia (fever)

Possible Side Effects of Lutetium Lu 177 Dotataate (Lutathera):

COMMON, SOME MAY BE SERIOUS

In 100 people receiving Lutetium Lu 177® more than 20 and up to 100 may have:

- Nausea
- Vomiting
- Fatigue

OCCASIONAL, SOME MAY BE SERIOUS

In 100 people receiving Lutetium 177® from 4 to 20 may have:

- Diarrhea
- Abdominal Pain
- Decreased appetite
- Headache
- Dizziness
- Hair loss

RARE, AND SERIOUS

In 100 people receiving Lutetium 177®, 3 or fewer may have:

- Muscle pain
- Bone pain
- Leg swelling
- Kidney failure
- Bone marrow failure

Additional Drug Risks

The study drugs used in this study could be very harmful to an unborn or newborn baby. There may be some risks that doctors do not yet know about. It is very important that subjects check with the study doctor about what types of birth control or pregnancy prevention to use during the study and for 6 months after they have completed the study.

The study drug could interact with other drugs. Rarely, there are problems getting enough supplies of the study drug.

Blood draw risks

Some of the risks from drawing blood from the arm may include pain, bruising, soreness, light-headedness or fainting, bleeding and rarely, infection.

Imaging Risks

The gallium 68 dotataate scan that subjects get in this study will expose them to low amounts of radiation. Every day, people are exposed to low levels of radiation that come from the sun and the environment around them. This type of radiation is called "background radiation." No one knows for sure whether exposure to these low amounts of radiation is harmful to the body.

Other Risks and Precautions

Lutetium Lu 177 Dotataate, a beta- and gamma particle-emitting pharmaceutical, is a radioactive therapeutic agent. Though the external radiation exposure associated with Lutetium Lu 177 Dotataate is low, care must be used to keep body fluids from coming in contact with family members or caregivers. The study doctor will give subjects information on the good hygiene practices to follow to minimize radiation exposure from bodily fluids to household members and caregivers. Some of the precautions include using disposable gloves when wiping up blood, urine, stools, or vomit, or when handling stained clothes. Clothing soiled with Lutetium Lu 177 Dotataate or fecal matter or urine should be washed promptly and separately from other clothing. Subjects will be advised to use the same toilet each time they use the bathroom in their home, and if possible, use a different toilet than other members of your household. They will also be advised to sit down on the toilet to urinate to keep urine from splashing or spraying. They will be asked to follow these guidelines for at least 30 days after each Lutetium Lu 177 Dotataate treatment. Flush the toilet a few times after each use.

There is always a chance that any medical treatment can be harmful. In addition to risks described in this consent, subjects may experience a previously unknown risk or side effect.

Conventional therapies such as radiation and chemotherapy are not effective in the treatment of neuroendocrine tumors. First-line systemic therapy usually consists of a somatostatin analogue for control of both hormonal secretion and tumor growth. With the exception of Everolimus and Lutetium Lu 177 Dotataate for the treatment of nonfunctional NETs, no standard second-line systemic treatment options are currently available.

Although the clinical benefit of Telotristat and Lutetium Lu 177 Dotataate has not yet been established, the intent of offering this treatment is to provide a possible therapeutic benefit, and thus the patient will be carefully monitored for tumor response and symptom relief in addition to safety and tolerability.

Radiolabeled somatostatin analogue Lutetium Lu 177 Dotataate is a beta- and gamma-emitting radionuclide. Radiolabeled somatostatin analogues provide a means of delivering targeted radiation with a high therapeutic index to tumors that express somatostatin receptors. Data from nonrandomized trials of Lutetium Lu 177 Dotataate have consistently shown high response rates and long durations of median progression-free survival in heterogeneous patient populations with gastroenteropancreatic neuroendocrine tumors. The NETTER-1 trial validates these early-phase data in the context of a prospective, randomized trial. In summary, Lutetium Lu 177 Dotataate resulted in markedly longer progression-free survival than high-dose octreotide LAR and was associated with limited acute toxic effects in a population of patients who had progressive neuroendocrine tumors that originated in the midgut.

We hypothesize that inhibition of serotonin production will lead to cytostatic effect on neuroendocrine tumors and will complement anti-tumor activity of lutetium 177 dotataate. We anticipate our proposed combination will result in improved treatment efficacy as reflected by improved 20-month PFS as compared to historical control.

#### Available Alternative Opportunities/Treatments

Describe alternative treatments or opportunities that might be available to those who choose not to participate in the study, and which offer the subject equal or greater advantages. If applicable, this should include a discussion of the current standard of care treatment(s).

Subjects can get the usual treatment for this type of cancer without being on study. They can participate in another study, if one is available. They can receive only palliative care or refuse all treatment.

The usual approach for patients who are not in a study is treatment with Lutetium Lu 177 Dotataate or everolimus, which are both approved by the Food and Drug Administration (FDA). Everolimus is able to keep the disease stable in 50 out of 100 treated patients for about 11 months. Lutetium Lu 177 Dotataate is able to keep the disease stable in 50 out of 100 treated patients for about 30-35 months.

[Back to Top](#)

#### Records, Privacy, and Confidentiality

Specify where the data and/or specimens will be stored and how the researcher will ensure the privacy and confidentiality of both. Specify who will have access to the data/specimens and why they need access.

Describe how data will be managed after the study is complete:

- If data/specimens will be maintained, specify whether identifiers will be removed from the maintained information/material.
- If identifiers will not be removed, provide justification for retaining them and describe how you will protect confidentiality.
- If the data/specimens will be destroyed, verify that this will not violate [retention policies](#) and will adhere to applicable facility requirements.

If this study will use de-identified data from another source, describe what measures will be taken to ensure that subject identifiers are not given to the investigator.

If applicable, describe procedures for sharing data/specimens with collaborators not affiliated with UK.

For additional considerations:

[Return of Research Results or Incidental Research Findings](#)

[HIPAA policies](#)

[FERPA policies](#)

[Procedures for Transfer agreements](#)

[Information regarding multi-site studies](#)

[NIH Genomic Data Sharing \(GDS\) Policy](#)

[Digital Data](#)

Subject specimens will not be collected for research purposes.

Return of Research Results or Incidental Findings (if applicable): N/A

Confidentiality of medical information is discussed at length in the informed consent. Subjects are made aware of what data will be collected, where it is stored and who has access to the information. Study data may be published or shared with other researchers, but the identity and medical history of each study participant will remain strictly confidential. Representatives of University of Kentucky, the National Institutes of Health, the Food and Drug Administration (FDA), other regulatory agencies, the Institutional Review Board (IRB), and Study Investigators reserve the right to review the study data and medical records relating to this research study. During the study, information will be collected to assess compliance with the study requirements. These records will be used by the FDA, the IRB, and the Investigator(s) in connection with complying with their obligations relating to this study. The records will not be used for any other purposes or disclosed to any other party without the subject's permission. All records will be coded with an identification number to protect their identity. All data stored is on site at UK Markey Cancer Center Clinical Research Organization in locked facilities, and with limited access to records by designated research staff. All research records will be held for a minimum of six years following completion of the study.

Patients enrolled in the study will be evaluated clinically and with standard laboratory tests before and at regular intervals during participation in this study. Safety will be assessed by physical examinations, clinical chemistry, and hematology tests and monitoring of adverse events. Adverse event reporting is mandatory from the date of the first study drug administration through 30 days following the

last dose of the study drug. Adverse events which occur prior to the first study drug administration will be captured in the patient's medical history. Laboratory, vital signs, or ECG abnormalities are to be recorded as Adverse Events only if they are medically relevant. The severity of adverse events will be assessed using National Cancer Institute Common Terminology Criteria for Adverse Events (NCI CTCAE), Version 5.0. Additionally, guidelines for AE's will comply with the University of Kentucky's IRB requirements. Confidentiality of medical information is discussed at length in the informed consent. To assure necessary medical intervention in the event of an adverse experience, patients are asked to notify their physician in the event of any adverse experience in the consent.

The patients are interviewed at each clinic visit by the research staff and are specifically asked if they have had any adverse experiences. Adverse events from ongoing studies are reviewed as the sponsor submits them to the PI and if necessary patients are contacted concerning any new information; and the information is added to the "Risks and/or Discomforts" section of the consent form.

**UK IRB policies state that IRB-related research records must be retained for a minimum of 6 years after study closure. Do you confirm that you will retain all IRB-related records for a minimum of 6 years after study closure?**

Yes  No

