## 1.2 Secondary Objectives:

1.2.1 To determine the overall response rate (ORR) by Response Evaluation Criteria In Solid Tumors (RECIST, v1.1) at 6 and 12-months post initiation of therapy

1.2.2 To establish the safety profiles of the combination of Telotristat (two dose levels, 250 mg PO TID and 500 mg PO TID) and Lutetium Lu 177 Dotataate

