## 9. STATISTICAL CONSIDERATIONS

### 9.1 Study Design/Endpoints

This is an open label, randomized, parallel arm, Phase II trial of two dose levels of Telotristat (250 mg TID and 500 mg TID) in combination with Lutetium Lu 177 Dotatate (Lutathera). The primary endpoint of the study is 20-month PFS. The study is designed to test a non-inferiority hypothesis for one proportion (proportion of patients had 20-month progression-free) for each arm separately. No interim analysis will be performed. All patients will be followed up to 36 months after the study enrollment. An intent-to-treat analysis will be performed and patients who drop-out prior to 20 months of follow-up will be deemed non-evaluable for the primary objective and excluded from primary objective analysis. PFS distribution and median PFS will be estimated using Kaplan-Meier method based on 36 months follow-up data.

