### 9.3 Analysis of Primary Endpoint

Hypothesis testing based on non-inferiority of PFS rate at 20 months will be performed for each arm using an exact test for one proportion. Furthermore, PFS will be estimated using the Kaplan Meier method and estimates at 20 months, other specific time points and 95% confidence interval will be calculated. Survival analysis models such as Cox regression will also be considered.

An intent-to-treat analysis will be initially performed wherein all patients who received at least one dose of the treatment regimen is included in the analysis. For the primary endpoint of PFS at 20 months, patients who drop-out and are not evaluated for the 20 month time point will be considered non-evaluable. Subjects will be followed for up to 36 months in order to capture significant events and median PFS (secondary endpoint) estimates.

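### Mandatory adverse-event reporting ends 30 days after the last dose of an unnamed one of two drugs, and nothing requires later serious or treatment-related events to be recorded up to month 36

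*Combined protocol and SAP*

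**What the plan says.** The reporting rule is in the IRB application part of the combined document, under Records, Privacy, and Confidentiality: "Adverse event reporting is mandatory from the date of the first study drug administration through 30 days following the" "last dose of the study drug" (one sentence, broken across a page). It does not say which drug is meant. Research Procedures and Costs to Subjects both attach the singular term to Telotristat. The Study Drug Information section lists Telotristat and Lutathera together, and Section 9.4.1 defines the safety population with the plural.

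Follow-up is longer. Section 9.1 states "All patients will be followed up to 36 months after the study enrollment", and Section 9.3 gives the purpose: "Subjects will be followed for up to 36 months in order to capture significant events and median PFS (secondary endpoint) estimates". Significant events are not defined.

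Safety is a secondary objective, 1.2.2: "To establish the safety profiles of the combination of Telotristat" at two dose levels with Lutathera. It has no time horizon. Section 9.4.1 promises toxicity tables by arm without stating a period. Section 9.7.1 makes patients evaluable for toxicity from their first Telotristat treatment and gives no end.

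The Drug Risks text places "Kidney failure" and "Bone marrow failure" among the rare and serious risks of Lutathera, at 3 or fewer per 100 people, with no time of onset.

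**The concern.** There are two separate problems.

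The first is the anchor. Two data managers could close the same patient's window on different dates, one counting from the last Telotristat dose and the other from the last Lutathera dose. Under the Telotristat reading, a patient who stops Telotristat early leaves mandatory reporting 30 days later even if Lutathera continues. The arms differ only in Telotristat dose, so if stopping patterns differ by dose, the arms would also differ in the time over which events must be reported. Section 9.4.1 tabulates by arm without fixing that time.

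The second is the interval between the close of the window and month 36. Patients are still in follow-up, but no stated rule requires a serious or treatment-related event to be recorded. The two organ failures named above are rare and serious, so one or two unrecorded cases could change the safety table of a small arm.

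**Working it through.** The plan gives no figure for the share of follow-up covered by adverse-event reporting, so there is none to reproduce.

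**Inputs**
- Window: first dose to last dose plus 30 days (Records, Privacy, and Confidentiality). 30 days = 30/30.4375 = 0.99 months.
- Follow-up: up to 36 months from enrolment (Sections 9.1 and 9.3).
- Patients per arm: 35 (Section 9.2; 33/(1 − 0.05) = 34.7, rounded up).
- Listed frequency: 3 or fewer per 100 (Drug Risks).
- T, the months from enrolment to the last dose of the anchor drug, is not in the available text. The study calendar is an attachment that is not reproduced. T is therefore an assumption shown over a range, with the first dose taken as at enrolment.

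**Step 1: anchor.** Let A be the month of the last Telotristat dose and B that of the last Lutathera dose. If Telotristat is the anchor, the window closes at A + 0.99. Whenever B is later than that, Lutathera is given outside mandatory reporting. This needs no value for T. If the window runs from the later of A and B, the case cannot arise.

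**Step 2: coverage.** Covered months = min(36, T + 0.99). Uncovered share = 1 − covered/36.

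| T (months, assumed) | Covered months | Covered share | Uncovered share |
|---|---|---|---|
| 6 | 6.99 | 19.4% | 80.6% |
| 12 | 12.99 | 36.1% | 63.9% |
| 17 | 17.99 | 50.0% | 50.0% |
| 24 | 24.99 | 69.4% | 30.6% |
| 30 | 30.99 | 86.1% | 13.9% |
| 35 | 35.99 | 100.0% | 0.0% |

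Half of the 36 months is uncovered when T + 0.99 = 18, that is T = 17.01.

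**Step 3: person-time, as a ceiling.** With 35 per arm all followed to month 36 and the window rounded to one month, uncovered patient-years per arm = 35 × (35 − T)/12. This is 84.6 at T = 6, 67.1 at T = 12 and 32.1 at T = 24. Section 9.2 allows for 5% drop-out, so actual values would be lower. The application's Project Information caps enrolment at 12, against 70 in Section 9.2. With 6 per arm the same formula gives 14.5, 11.5 and 5.5.

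**Step 4: expected cases.** At the top of the listed frequency, each failure would be expected in at most 35 × 0.03 = 1.05 patients per arm, or 6 × 0.03 = 0.18 with 6 per arm, at any time. How many would fall after the window cannot be computed, because no onset times are given.

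**Step 5: other safety text.** Research staff ask about adverse experiences at clinic visits, and clinical and laboratory checks continue at intervals during participation. Neither says that an event found after the window is recorded. Section 9.7.1 is open-ended where the reporting rule is closed, so the end date of the toxicity tables is undefined.

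**The case against.** The best defence is that the rule says when reporting is mandatory, not that later information is thrown away. Patients are asked about adverse experiences at their visits, toxicity evaluability has no end date, adverse-event handling is to follow the university's IRB requirements, and the quality assurance committee reviews serious events at its meetings. The significant events of Section 9.3 may simply be progression events; if they are safety events, that section already intends their capture to month 36. The singular term may plainly mean Telotristat, given its use elsewhere. The IRB application is also not the whole protocol: apart from the objectives, only Section 9 of the numbered text is available, and a fuller rule may stand in another section or in the calendar.

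Much of this stands. A reader might infer that the safety objective misses most of the follow-up. That requires a last dose before about month 17, and the documents give no treatment duration; with long-term Telotristat as the anchor, coverage could be complete. A reader might also infer that late safety data are discarded, or that rates per arm will be understated. The text supports neither: it is silent on later events, gives no onset times and sets no horizon for the safety objective.

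The rule itself remains a problem. Asking about events is not a requirement to record them, and an evaluability statement without an end date does not extend a reporting window that has one. Reading the term as Telotristat settles the anchor but exposes the case in which Lutathera outlasts it.

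**Conclusion.** The point holds in a limited form, as a cheap improvement. Followed as written, the rule leaves the anchor drug unnamed, can close mandatory reporting while Lutathera is still being given if Telotristat is the anchor and stops first, and requires no record of later serious or treatment-related toxicity. The uncovered part of the 36 months ranges from about 81% with a last dose at month 6 to nothing from about month 35. That range rests on assumed treatment durations and on first dose at enrolment. The patient-year figures are ceilings. Safety rates per arm may be understated; whether they are depends on event timing that the documents do not give. The primary endpoint is unaffected.

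**What to change.** Reconcile the reporting sentence under Records, Privacy, and Confidentiality with Sections 9.3 and 9.7.1, as follows:

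- Keep the 30-day window for all adverse events, but count it from the last dose of whichever of the two drugs is given later.
- From then to month 36, record treatment-related serious adverse events and any kidney failure or bone-marrow failure at the follow-up visits already planned.
- In Section 9.4.1, tabulate these later events by arm, separately from events within the window.
- In Section 9.3, say whether significant events include safety events.

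This is data capture only, with no new procedure, test or change in care. It costs a few sentences, some form fields and modest extra data entry, on the assumption that the visits in the unreproduced study calendar run through follow-up. If a fuller adverse-event rule already stands in protocol sections outside the available text, a cross-reference to it is enough.

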#### Attachments

## Research Procedures

Describe how the research will be conducted.

- What experience will study participants have?
- What will study participants be expected to do?
- How long will the study last?
- Outline the schedule and timing of study procedures.
- Provide visit-by-visit listing of all procedures that will take place.
- Identify all procedures that will be carried out with each group of participants.
- Describe deception and debrief procedures if deception is involved.

Differentiate between procedures that involve standard/routine clinical care and those that will be performed specifically for this research project. List medications that are explicitly forbidden or permitted during study participation.

All of the procedures to be carried out are illustrated in the attached study calendar.

These experimental procedures include the following: a) obtaining informed consent, b) evaluating for inclusion and exclusion criteria, c) assessing adverse events by infusion center nurse, research nurse, or other qualified healthcare professional and d) recording and using the clinical data outlined in flowcharts to develop the data base for this study.

Additional research procedures include:

- Administration of study drug, Telotristat (Xermelo)
- Data collection via questionnaires: EORTC QLQ-C30 (Core) and QLQ-GI.NET21

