## **9.4 Analysis of Secondary and Exploratory Endpoints**

### **9.4.1 Analysis of Secondary Endpoints**

ORR will be assessed by RECIST v1.1 of CT/MRI scans completed at 6 and 12 months post-initiation of study treatment, and will be estimated along with 95% binomial confidence intervals.

Comparison of pre vs. follow-up measurements of urinary 5-HIAA and QOL will be performed using paired t-tests or linear mixed models for repeated measurements. Carcinoid syndrome assessment of diarrhea and flushing will be summarized at each time point of follow-up and paired comparisons will be performed using non-parametric Wilcoxon signed-ranks test or paired test for proportions.

Safety data for this combination will be summarized in a descriptive table. All patients who received study drugs will be included in the safety analysis. The maximum grade of toxicity for each AE category of interest will be recorded for each patient and the summary results will be tabulated by category and grade. We will describe all serious ( $\geq$  grade 3) toxicity events on a patient-by-patient basis. Frequency and incidence tables of toxicity and AEs will be generated for each treatment arm.

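### Laboratory abnormalities must pass an undefined relevance test before they are graded, and no analysis of the collected laboratory values is specified, so the safety tables can under-count asymptomatic laboratory toxicity

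*Combined protocol and SAP*

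**What the plan says.** The recording rule is in the IRB application, under Records, Privacy, and Confidentiality: "Laboratory, vital signs, or ECG abnormalities are to be recorded as Adverse Events only if they are medically relevant". The next sentence sets the scale: "The severity of adverse events will be assessed using National Cancer Institute Common Terminology Criteria for Adverse Events (NCI CTCAE), Version 5.0". The same section makes laboratory testing part of the safety assessment: "Safety will be assessed by physical examinations, clinical chemistry, and hematology tests and monitoring of adverse events". It says these tests are done before and at regular intervals during participation.

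Protocol section 9.4.1 then sets out the safety summary: "The maximum grade of toxicity for each AE category of interest will be recorded for each patient". It adds that toxicity of grade 3 or higher will be described patient by patient, and that "Frequency and incidence tables of toxicity and AEs will be generated for each treatment arm". It names no table of laboratory grades, shifts or values.

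On who assesses events, Research Procedures lists "assessing adverse events by infusion center nurse, research nurse, or other qualified healthcare professional". On blinding, section 9.1 states: "This is an open label, randomized, parallel arm, Phase II trial of two dose levels of Telotristat". Objective 1.2.2 is to establish the safety profiles of the combination at the two telotristat doses.

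**The concern.** Two standards are in play. In 9.4.1 the severity grade decides what is described. In the application a judgement of relevance comes first, and only what passes it becomes an adverse event and receives a grade. A laboratory value that would be grade 3 or higher, but that staff regard as unimportant, meets the reporting threshold in 9.4.1 and yet may never be recorded as an event to report.

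This matters here because several of the risks that the documents list are laboratory findings. The telotristat list includes raised GGT, ALT, AST and alkaline phosphatase. If such changes cause no symptoms, whether they reach the tables depends on an undefined judgement. Staff know the arm and the tables are shown by arm, so a difference in how that judgement is applied could look like a dose difference, or hide one.

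**Working it through.** The plan states no figure for the safety endpoint, so there is none to reproduce. The primary design (33 evaluable and 35 enrolled per arm, section 9.2) is not affected.

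**Step 1: follow one laboratory value through the text.**
- Collected? Yes. Chemistry and hematology are safety assessments (Records, Privacy, and Confidentiality).
- Recorded as an adverse event? Only if judged relevant (same section). No criterion is supplied.
- Graded? The scale is applied to the severity of adverse events, so a value that fails the filter has no stated route to a grade.
- Tabulated? 9.4.1 works from AE categories and from tables of toxicity and AEs. No laboratory-based table is specified. Section 9.7.1 says when patients become evaluable for toxicity, but does not say that toxicity is derived from laboratory data.

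Compared with grading every collected value, a filter placed before grading can only lower the counts or leave them unchanged.

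**Step 2: illustrate the size.** The true rates *t* and the capture fractions *c* below are assumptions; the documents give neither. The planned 35 per arm is from section 9.2. The Project Information section gives a maximum of 12 subjects in total; a smaller enrolment changes the patient counts but not the percentages.

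Recorded rate = *t* × *c*; expected patients recorded = 35 × *t* × *c*.

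| True rate (patients of 35) | Capture 90% | Capture 70% | Capture 50% |
|---|---|---|---|
| 10% (3.5) | 9% (3.15) | 7% (2.45) | 5% (1.75) |
| 20% (7) | 18% (6.3) | 14% (4.9) | 10% (3.5) |
| 40% (14) | 36% (12.6) | 28% (9.8) | 20% (7) |

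**Step 3: compare the arms.** With equal true rates, the false difference is *t* × (*c*₁ − *c*₂). For capture of 90% against 70%:
- *t* = 10%: 0.10 × 0.20 = 2 points
- *t* = 20%: 0.20 × 0.20 = 4 points
- *t* = 40%: 0.40 × 0.20 = 8 points

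With equal capture and equal true rates the false difference is 0. With equal capture and unequal true rates, a real difference shrinks: true rates of 40% and 20% with 70% capture in both arms give 0.70 × 20 = 14 points instead of 20.

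**Step 4: what the documents say about frequency.** The Lutathera risk list puts kidney failure and bone marrow failure at 3 or fewer per 100, so at most 35 × 0.03 = 1.05 patients per arm. The telotristat list puts raised GGT at 1 to 10 per 100, or 0.35 to 3.5 patients of 35, with no grade stated. For ALT, AST and alkaline phosphatase no frequency is reported. These are not rates of grade 3 or higher laboratory values and do not fix *t*. They give no support for preferring the upper rows of the table.

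**The case against.** The strongest reply is that the recording rule governs what is called an adverse event and does not decide which data are analysed. Chemistry and hematology stand in the safety assessment in their own right, and 9.4.1 speaks of toxicity as well as AEs, so laboratory tables are not excluded. That stands: a reader might infer that laboratory values can reach the safety analysis only through the relevance filter, and the text does not go that far. But it commits to no such table.

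A reader might also infer that marrow or kidney failure will go missing. The documents do not support this. Both are listed as rare and serious, and it is implausible that staff would call either irrelevant. The exposure is to asymptomatic laboratory change, most plausibly of low grade.

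Nor do the documents say that the investigator makes the call. The rule names no one, and Research Procedures assigns AE assessment to nurses or other qualified professionals. Because the trial is open label, the point about knowledge of the arm holds for them too.

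The quality assurance committee described under Data and Safety Monitoring is a partial safeguard. It sees serious events and dose modifications, so laboratory toxicity that changes treatment should surface there. Laboratory values themselves are not on its list.

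Finally, only section 9 of the protocol is supplied, the rule sits in a summary answer on an application form, and AE guidelines are also said to follow IRB requirements that are not shown. A definition may exist elsewhere. If it does, the first half of the point becomes a missing cross-reference; the absence of a laboratory analysis in 9.4.1 remains.

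**Conclusion.** The point holds as a cheap improvement. On the supplied text, an undefined filter precedes grading, 9.4.1 promises all toxicity of grade 3 or higher, and no analysis of the collected laboratory values is specified as a backstop. The tables can under-count asymptomatic laboratory toxicity, and uneven judgement could distort a comparison of arms that is descriptive only; no formal test of safety between arms is planned.

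It would go too far to say that the tables will under-count or that the toxicity rates will be wrong. That requires staff to dismiss values of consequence, and nothing in the documents says they would. Objective 1.2.2 names no organ system; liver, marrow and kidney come from the risk lists.

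The size cannot be computed from the documents. The 2 to 8 points shown above rest wholly on assumed true rates of 10% to 40% and assumed capture of 90% against 70%. Sample size, significance level and power do not change.

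**What to change.** - In 9.4.1, derive CTCAE v5.0 grades directly from the collected hematology and chemistry values, for every parameter that the scale grades, whether or not an adverse event was reported. Show baseline grade against worst post-baseline grade by arm, and list all values of grade 3 or higher by patient. State which value is baseline and what period counts as post-baseline; the plan's existing AE reporting window would serve.
- Reconcile the recording rule in Records, Privacy, and Confidentiality with the grade 3 or higher reporting threshold in 9.4.1. If an AE section of the protocol already defines medical relevance, cite it in both places.

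The cost is a short addition to 9.4.1 and one programmed table with a listing, from data already collected. No new patient tests are needed, and no treatment rule is touched. The downside is one more table and somewhat higher reported toxicity rates, so the report should say which tables come from laboratory values and which from recorded adverse events.
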